5.2 Interim Analyses

Interim analysis is not planned.

Initial analysis is planned at the last patient's 6 month follow-up completion (primary analysis for submission) and the second analysis (additional analysis) at 12 month follow-up completion. Final analysis (additional analysis) is planned once all follow-ups (24month follow-up) required by the study are completed.

5.3 Subgroup Analyses

Sub-group analysis will be completed, such as analysis by BSJ003W size, Sex, Age(<75, ≥75) and ability to discontinue Warfarin, CHADS₂ score(1-3, 4-6), CHA₂DS₂-VASc score (1-3, 4-9), and HAS-BLED score (1-3, 4-9), AF pattern (Paroxysmal, Persistent +Permanent +Paced), AF ablation, LVEF (Above Median, below Median), history of stroke/TIA, abnormal renal function, chronic dialysis, for the primary and secondary endpoints, appropriately. LAAC by Baseline covariates (raw category) will be displayed.

5.4 Justification of Pooling

Not applicable due to single-arm study.

5.5 Multivariable Analyses

Univariate and multivariate analyses will be performed to assess predictors for primary and secondary endpoints appropriately.

Unknown is counted as missing.

Planned covariates at start are followings listed;

AGE at IC (<75, ≥75),
Sex (Male, Female),
Body weight (<60kg, ≥60kg)
BSJ003W size (21mm+24mm+27mm, 30mm+33mm),
AF pattern (Paroxysmal, Persistent +Permanent +Paced)
AF onset (<1 year, ≥1year)
LVEF (Above Median, below Median)
Warfarin discontinuation (Yes/No),
History of Stroke/Ischemic stroke/Hemorrhagic stroke /TIA (Yes/No),
CHADS₂ score (1-3, 4-6)
CHA₂DS₂-VASc score (1-3, 4-9)
HAS-BLED score (1-3, 4-9)
LAA ostium diameter (Above Median, below Median),
LAA length (Above Median, below Median),
Previous AF ablation (Yes/No),
MI (Yes/No)
Hypertension (Yes/No)
Congestive Heart Failure (Yes/No)
NYHA (I/II, III)
LV dysfunction (Yes/No)
Peripheral Artery Disease (Yes/No)
Diabetes (Yes/No),
Abnormal Renal Function (Yes/No),
Chronic Dialysis (Yes/No),

Warfarin naïve (Yes/No)

From those covariates, as a result, highly skewed or rare frequency cases are deleted, and correlated variables are combined to one variable and then entered into the model.

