Additional Endpoints	
Device performance:
 
 • Technical Success defined as successful delivery and release of BSJ003W into the LAA including successful recapture and retrieval if necessary. 
Safety endpoints:
 
 • Occurrence of reportable adverse events • Occurrence of all-cause mortality 
Effectiveness endpoints:
 
 • Individual occurrence of all-cause death, ischemic stroke,

A study to confirm the safety and effectiveness of the BSJ003W in Japanese patients with non-valvular atrial fibrillation at increased risk of thromboembolism in Japanese clinical environment									
	
hemorrhagic stroke, systemic embolization, cardiovascular death (including unexplained cause) at 6-month, 12-month and 24-month.
 
 • Warfarin discontinuation rate at 45 days, 6-month and 12-month • Severity of stroke assessed by NIH Stroke Score, Modified Rankin Scale Score, and Barthel Index 
Other endpoint:
 
 • EQ-5D 								
Required Medication Therapy	
  
 Visit	Medication	
   
 Implant through 45-day visit	ASA+ Warfarin	
 
 45-day visit through 6-month visit	ASA+ Thienopyridine	
 
 Following the 6-month visit	ASA	
  
 
Warfarin therapy should be appropriately monitored and adjusted so as to achieve a therapeutic INR of 2.0- 3.0. For a subject who are 70 years old or older, a therapeutic INR of 2.0 – 2.6 is recommended considering the high risk of major bleeding. Subjects should remain on warfarin until the 45-day TEE evaluation has shown adequate seal of the LAA. If the LAA is not adequately sealed, the subjects should be on warfarin and Aspirin therapy.
	Visit	Medication	Implant through 45-day visit	ASA+ Warfarin	45-day visit through 6-month visit	ASA+ Thienopyridine	Following the 6-month visit	ASA
Visit	Medication								
Implant through 45-day visit	ASA+ Warfarin								
45-day visit through 6-month visit	ASA+ Thienopyridine								

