Following the 6-month visit	ASA								
Follow-up Schedule	
Study procedures and follow-up visits will occur as follows:
 
 • Informed consent • Screening • BSJ003W Implant • 45-day Follow-up (45 ± 15 days) • 6-Month Follow-up (180 ± 15 days) • 12-Month Follow-up (365 ± 30 days) • 18-Month Follow-up (540 ± 60 days) • 24-Month Follow-up (730 ± 60 days) 								
Study Duration	
The duration of the study is expected to last approximately 3 years. The duration of individual subject participation is expected to last approximately 2 years.
								

A study to confirm the safety and effectiveness of the BSJ003W in Japanese patients with non-valvular atrial fibrillation at increased risk of thromboembolism in Japanese clinical environment	
Key Inclusion Criteria	
 1. The subject is Japanese, over 20 years old and provides written informed consent to participate in the trial 2. The subject has documented paroxysmal, persistent or permanent non-valvular atrial fibrillation 3. The subject has a calculated CHA₂DS₂-VASc score of 2 or greater and is recommended for long-term oral anti-coagulation therapy 4. The subject is deemed by their physicians to be suitable for anticoagulant therapy and have an appropriate rationale to seek a non-pharmacologic alternative to warfarin 5. The subject is eligible to come off warfarin therapy if the LAA is sealed (i.e. the subject has no other conditions that would require warfarin therapy).

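### Warfarin discontinuation, a post-implant status with no stated time point, is a subgroup and candidate predictor for outcomes that normally come before it or may determine it

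*SAP*

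**What the plan says.** Section 5.5 sets the scope of the models: "Univariate and multivariate analyses will be performed to assess predictors for primary and secondary endpoints appropriately". Its list of starting covariates includes "Warfarin discontinuation (Yes/No", with no date or visit attached. On incomplete values it says only "Unknown is counted as missing". It then states a screening rule: covariates that turn out highly skewed or rare are deleted, and correlated ones are merged into one before modelling.

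Section 5.3 names "ability to discontinue Warfarin" as a subgroup factor for the primary and secondary endpoints, also without a time point.

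Three parts of section 1 (Protocol Summary) bear on when this status arises:

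- Key inclusion criterion 5: "The subject is eligible to come off warfarin therapy if the LAA is sealed".
- Required medication therapy: "Subjects should remain on warfarin until the 45-day TEE evaluation has shown adequate seal of the LAA". Without adequate seal, warfarin and aspirin continue.
- Follow-up schedule: "45-day Follow-up (45 ± 15 days".

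The same section lists discontinuation as an outcome in its own right: "Warfarin discontinuation rate at 45 days, 6-month and 12-month".

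**The concern.** A subgroup factor or predictor should be fixed before the outcome it is meant to explain. Warfarin discontinuation is not a baseline trait here. Eligibility to stop is an entry requirement, so it cannot separate subjects at baseline. What can separate them is whether they actually stopped, and the plan places that decision at the 45-day TEE. For outcomes that occur earlier, the analysis would use a later status to explain an earlier event. For 45-day closure, the outcome may itself decide the group.

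What is at stake is interpretation. Section 2 allows the specified analyses to be used in presentations and manuscripts. A table showing discontinuation as a predictor of peri-procedural events, or of bleeding in the first 45 days, would invite a reading that the timing cannot support.

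**Working it through.** The point rests on no figure stated in the plan, so there is none to reproduce. The check compares the time at which the status is fixed with each outcome window.

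**Inputs (section 1 unless noted)**
- 45-day visit: 45 ± 15 days. 6-month visit: 180 ± 15 days.
- Endpoint 1: implant to day 7 or hospital discharge, whichever is later (also section 3.1).
- Major bleeding windows: 0–45 days, 45 days–6 months, 6–24 months.
- Endpoint 2: all data up to the last patient's 6-month visit.
- Endpoint 3: closure (peri-device flow ≤ 5 mm on TEE) at 45 days and 6 months.

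**Step 1. When the planned stop can occur.** Earliest 45 − 15 = day 30; latest 45 + 15 = day 60.

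**Step 2. Endpoint 1.** 30 − 7 = 23 days. The day-7 limit falls at least 23 days before the planned stop. The whole window comes first unless discharge is later than the 45-day visit.

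**Step 3. 0–45-day bleeding.** With a day-30 visit, 30/45 = 67% of the window comes first. With a visit at day 45 or later, 45/45 = 100% does.

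**Step 4. Endpoint 2.** For a subject followed only to the 6-month visit (day 165 to 195), the share of follow-up before the decision is:
- smallest: 30/195 = 15%
- at target days: 45/180 = 25%
- largest: 60/165 = 36%

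The share is smaller for subjects followed longer.

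**Step 5. 45-day closure.** Warfarin is to stop after adequate seal and continue without it. The SAP does not define adequate seal. If it means effective closure, and practice follows the rule exactly, the status repeats the outcome. One non-closed subject among n then gives complete separation with a Fisher exact p of 1/n: 1/36 = 0.028, or 1/40 = 0.025. That result would arise by construction.

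**Step 6. Later outcomes.** With the status fixed at the 45-day visit, at most 60 − 45 = 15 of the 180 − 45 = 135 days in the 45-day–6-month bleeding window precede it (15/135 = 11%). The 6–24-month window is clear of it. The 6-month TEE follows by at least 165 − 60 = 105 days. Its link to the status is indirect, through the 45-day seal.

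**Step 7. What the screening rule could do.** If the 99.3% expected closure rate (section 1, sample size) also held at 45 days and seal meant closure, about 40 × 0.007 = 0.28 subjects would be unsealed. The covariate could then be deleted as skewed. The rule depends on frequency and correlation, not timing, and it is stated only for the models in section 5.5.

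**The case against.** The strongest reply is that little depends on these analyses. Sections 3.1.1 and 3.2.1 state no hypotheses, and the success rule in section 3 uses only the safety and closure targets. Few events are expected: 40 × 0.022 = 0.88 for Endpoint 1 and 36 × 0.007 = 0.25 non-closures at 6 months. Hardly any predictor of these endpoints could be estimated. Both sections also say that the analyses will be done appropriately, which does not oblige the sponsor to run every pairing of covariate and endpoint. The screening rule may remove the variable from the models altogether.

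Most of this stands and limits the severity. It does not remove the point. Neither the qualifier nor the screening rule says which outcomes the variable may be used for, and the section 5.3 subgroups have no screen.

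A reader might go further in four ways that the documents do not support:

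- **A known bias.** It is tempting to infer that continuing subjects must look worse because early events prevent stopping. That requires early events to be coded as not discontinued, which the SAP does not say. A subject taken off warfarin early because of a bleed would push the other way. The calendar shares above describe order in time, not bias.
- **Closure fully sets the status.** This depends on an undefined term and on exact adherence to the rule.
- **Early deaths disappear from the trial.** They could drop out only of analyses split or adjusted by discontinuation. Endpoint 2 and all-cause mortality are reported separately.
- **The same fault in section 5.8.** Classifying other endpoints by closure there is descriptive and exploratory, and makes no claim of prediction.

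**Conclusion.** The concern holds in a limited form. As written, sections 5.3 and 5.5 allow a post-implant status with no time point to serve as subgroup and predictor for Endpoint 1, 67–100% of whose companion 0–45-day bleeding window also comes first, and for Endpoint 2, where 15–36% of follow-up precedes the decision in a subject followed only to 6 months. For 45-day closure the outcome may define the group; that part is an inference. Associations with these outcomes cannot be read as prediction.

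The conclusion assumes that subjects stop at the 45-day visit as planned, and that discharge does not extend beyond it. The size and direction of any bias cannot be derived from the SAP. Bleeding after day 45 is mostly unaffected if the status is fixed at the 45-day visit. The primary conclusion of the study is not affected. The change is worth making because it is simple and prevents a misleading table.

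**What to change.** Amend sections 5.3 and 5.5 as follows:

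1. Remove warfarin discontinuation as a subgroup and covariate for Endpoint 1, 0–45-day bleeding and 45-day closure.
2. For Endpoint 2 and for later bleeding, stroke or embolism, define the status at the 45-day visit. Use it only in a landmark analysis of subjects still in follow-up at that visit, counting only events after it.
3. For 6-month closure, use only the 45-day status and label it a possible proxy for the 45-day seal.

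This changes SAP wording only; treatment, data collection and sample size stay as they are. The cost is that early events and a few subjects leave these exploratory analyses, so they should be reported separately.

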5.6 Sensitivity Analysis for Missing outcome data

Sensitivity analyses for the binary primary effectiveness and/or safety endpoints assessment will be conducted to assess the impact of missing data on the result's robustness, if necessary. In addition to the use of the worst-case analysis, the tipping point analysis will be performed for the ITT analysis set to consider all combinations of present/absent for all subjects with missing primary outcome. No imputation will be made to the other endpoints/parameters unless specified.

5.7 Handling of Missing Date

For the analysis of adverse events or medication usage, missing and partial dates will be handled as shown below.

Partial Date Description	Action Taken
Entire onset date is missing	The procedure date will be used for the onset date.
The month and the day of the month are missing but the year is available	January 1 will be used for the month and day of the onset date. However, if the imputed date falls before the procedure date, then the procedure date will be used for the onset date.
Day is missing, but the month and year are available	The 1 st will be used as the day of the onset date. However, if the imputed date falls before the procedure date, then the procedure date will be used for the onset date.

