all-cause death, ischemic stroke, systemic embolism, or device- or procedure- related events requiring open cardiac surgery or major endovascular intervention such as pseudoaneurysm repair, AV fistula repair, or other major endovascular repair.

Percutaneous catheter drainage of pericardial effusions, snaring of an embolized device, thrombin injection to treat femoral pseudoaneurysm and nonsurgical treatments of access site complications are excluded from this endpoint.

2. The occurrence of composite events* including stroke (all/ ischemic/ hemorrhagic), systemic embolism and CV death (including unexplained cause) .

*All data collected up to the last patient's 6 months follow-up visit to be completed.

3. The rate of effective LAA closure* at 45 days and 6 months. Change in the rate between the two time points will also be analyzed.

*The effective LAA closure is defined as peri-device flow \leq 5mm demonstrated by TEE. TEE measurements will be assessed by independent Core Lab.

A study to confirm the safety and effectiveness of the BSJ003W in Japanese patients with non-valvular atrial fibrillation at increased risk of thromboembolism in Japanese clinical environment	
Secondary endpoints	
Safety endpoints:
 
 • The occurrence of major bleeding* at 0 – 45 days, 45 days – 6 months, 6 months – 24 months 
*Major bleeding is defined as per BARC bleeding definition type 3 or 5
 
 • Frequency of the following bleeding events at 0 – 45 days, 45 days – 6 months and 6 months – 24 months: • Clinically overt non-fatal bleeding* • All bleeding events 
*Clinically overt non-fatal bleeding is defined as per BARC bleeding definition type 2.
 
Effectiveness endpoints:
 
 • The occurrence of composite events* for effectiveness; stroke (all/ ischemic/ hemorrhagic), systemic embolism and CV death (including unexplained cause) 
*All data collected up to the last patient's 12 months and 24 months follow-up visits to be completed.
 
 • Effective LAA closure at 12-month and its time course until then. • The occurrence of ischemic stroke or systemic embolism (excluding 7 days after implanting or day after hospital discharge whichever is later) at 6 months, 12 months and 24 months.

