3.1 Primary Safety Endpoint (Endpoint 1)

Primary safety endpoint is the occurrence of one of the following events between the time of implant and within 7 days following the procedure or by hospital discharge, whichever is later:

all-cause death, ischemic stroke, systemic embolism, or device- or procedure-related events requiring open cardiac surgery or major endovascular intervention such as pseudoaneurysm repair, AV fistula repair, or other major endovascular repair.

Percutaneous catheter drainage of pericardial effusions, snaring of an embolized device, thrombin injection to treat femoral pseudoaneurysm and nonsurgical treatments of access site complications are excluded from this endpoint.

Similarities of this study results will be evaluated with foreign pivotal study results.

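### Section 5.7 moves partial onset dates to the procedure date even when the recorded month or year already proves an earlier onset

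*SAP*

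**What the plan says.** SAP Section 5.7 sets its scope in one sentence: "For the analysis of adverse events or medication usage, missing and partial dates will be handled as shown below". Its table has three rows.

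- Onset date entirely missing: "The procedure date will be used for the onset date".
- Only the year known: 1 January of that year is imputed.
- Month and year known: the first of that month is imputed.

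Both partial-date rows then end with the same override: "However, if the imputed date falls before the procedure date, then the procedure date will be used for the onset date".

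Nothing in the table compares the recorded month or year with that of the procedure, and no other section of the SAP qualifies the override. The table speaks only of an onset date. For medication usage, the natural reading is the start date.

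**The concern.** A date-imputation rule should fill a gap without contradicting what was recorded. Where the recorded part already places the onset before the procedure, the override replaces known information with a date known to be false.

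Medication is the clearer exposure. It is named in the scope, and some use before the procedure is to be expected: Section 5.5 lists "Warfarin naïve (Yes/No") as a covariate, so some subjects are presumably on warfarin already. Long-standing drugs are also the ones likely to carry only a year or a month. Under the rule they all become implant-day starts, prior use can no longer be told from new use by start date, and a start can fall after a recorded stop.

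For adverse events, a record dated wholly to an earlier month would become a day-0 event. It could then count in "Occurrence of reportable adverse events" as if it followed the procedure, or, if it is a bleed, in the first window of "The occurrence of major bleeding* at 0 – 45 days, 45 days – 6 months, 6 months – 24 months".

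**Working it through.** The SAP gives no figure to reproduce here, so the check applies the rule literally.

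**Inputs.** The rule is from Section 5.7. The procedure date of 20 May 2017 is an assumption for illustration.

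**Formula.** Imputed onset = the later of (a) the earliest date compatible with the record and (b) the procedure date. An onset is provably earlier when the *latest* date compatible with the record is still before the procedure.

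**Step 1. Single records.**

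| Recorded | Compatible range | Rule gives | Status |
|---|---|---|---|
| 2015 | 1 Jan – 31 Dec 2015 | 20 May 2017 | provably earlier, by 506 to 870 days |
| April 2017 | 1 – 30 Apr 2017 | 20 May 2017 | provably earlier, by 20 to 49 days |
| May 2017 | 1 – 31 May 2017 | 20 May 2017 | ambiguous |
| 2017 | 1 Jan – 31 Dec 2017 | 20 May 2017 | ambiguous |
| June 2017 | 1 – 30 Jun 2017 | 1 Jun 2017 (day 12) | later, floor not used |
| 2018 | 1 Jan – 31 Dec 2018 | 1 Jan 2018 (day 226) | later, floor not used |

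The first two rows are the defect. In the next two the floor is a reasonable choice.

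**Step 2. Conflict with a stop date.** A drug started in 2015 and stopped on 10 March 2017 gets a start of 20 May 2017. From 10 March to 20 May is 21 + 30 + 20 = 71 days, so the start falls 71 days after the stop.

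**Step 3. Share of partial medication starts affected.** Assume procedure dates spread evenly over 365 days and starts spread evenly over the W days before the procedure.

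- Year only: the mean time from 1 January to the procedure is 182 days, so the share provably earlier is (W − 182)/W. For W = 365, 730 and 1825 this is 50.1%, 75.1% and 90.0%.
- Month and year: the mean time from the first of the month to the procedure is 5373/365 = 14.7 days, so the share is (W − 14.7)/W: 96.0%, 98.0% and 99.2%.

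These are shares *of partial dates before the procedure*, not of subjects or of all records. The number of partial dates is not given.

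**Step 4. Adverse events between consent and implant, if collected.** An onset k days before the procedure (k up to 28) falls in an earlier calendar month for 12k of 365 procedure dates. Averaging over an assumed consent-to-implant gap:

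- 7 days: 12 × 4/365 = 13.2%
- 14 days: 12 × 7.5/365 = 24.7%
- 30 days: 50.9% by enumeration (k = 29 and 30 need the short month handled separately)

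The gap is not given, so this is a range under assumption for month-only dates.

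**Step 5. Would it be simpler to exempt medication starts from the floor?** No. The Protocol Summary schedules a change of regimen at the 45-day visit. Without the floor, a true day-45 start recorded by year only becomes 1 January of that year. That precedes the procedure unless day 45 falls in the next calendar year (45 procedure dates) or the procedure was itself on 1 January (1 date): (365 − 45 − 1)/365 = 319/365 = 87%. For day-0 and day-1 starts the shares are 364/365 and 363/365, both over 99%. New starters would look like prior users, which is the opposite error.

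**The case against.** The strongest reply is that no planned analysis is shown to use the false value.

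- The named medication endpoint is the warfarin discontinuation rate, which turns on stopping; Section 5.7 imputes only onset.
- Time in therapeutic range (Section 7.3.5) uses INR values between visits, not drug start dates.
- The warfarin-naïve covariate sits among baseline history items and may well be collected separately, in which case it is untouched.
- For a drug still in use at implant, a day-0 start gives the right status after implant.
- The adverse-event part is empty if collection begins at the procedure, a point normally left to the protocol.

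All of this stands, and it limits the consequence. It does not rescue the rule. Medication usage is expressly in scope, and a literal program would still write starts that the record contradicts, some of them after a recorded stop. Nor does the plan leave this to the programmer: Section 5.9 asks for an amended SAP before a planned analysis is changed, or a documented deviation afterwards.

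A reader might also infer that the rule hides late strokes, because an undated event, or one dated only to the procedure's own month or year, goes to day 0 and so leaves the secondary endpoint defined as "The occurrence of ischemic stroke or systemic embolism (excluding 7 days after implanting or day after hospital discharge whichever is later"). That is a different matter. Such records do not contradict day 0, and moving them there can only add events to Endpoint 1. Section 4.2 also provides for adjudication of important endpoints, and the SAP does not say whether Section 5.7 governs those event dates. The choice for ambiguous dates is defensible.

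**Conclusion.** The defect is real and lies in the stated rule: the procedure-date floor is unconditional and overrides recorded months and years that prove an earlier onset. Severity is low. The effect falls on medication-usage summaries and, only if events before implant are collected, on adverse-event summaries and bleeding windows.

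The illustrations (506 to 870 days late; a start 71 days after a stop) rest on an assumed procedure date. The percentages rest on evenly spread dates and apply only to partial dates, whose number is unknown.

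A reader might infer that the primary safety result is at risk, since its window runs from implant: "Primary safety endpoint is the occurrence of one of the following events between the time of implant and within 7 days following the procedure". The SAP does not support that. It does not say that events before implant are collected, and an event wrongly moved to day 0 could only raise the Endpoint 1 rate, by 1/40 = 2.5 points each, which is against the device. No primary endpoint, and no named secondary endpoint, is shown to change. A reader might likewise infer that the warfarin-naïve covariate is corrupted; the SAP does not say how it is derived, so that link is unproven.

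**What to change.** Amend Section 5.7 in two respects:

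1. Use the procedure date in place of an earlier imputed date only when the recorded month and year (or the year alone) are compatible with onset on or after the procedure. Otherwise keep the record as pre-procedure.
2. Never impute an onset later than a known end date.

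Keep the floor for ambiguous dates, including medication starts recorded in the procedure's own month or year. In the illustration, the 2015 and April 2017 records then stay pre-procedure, and the May 2017 and 2017 records still go to 20 May 2017 unless a known end date shows that they ended earlier.

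The cost is two or three lines of SAP text and two conditions in the date program. No sample size, performance target or endpoint definition changes.
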